5.2.4. Secondary Efficacy Analysis

The secondary efficacy endpoints and methods of analysis are:

5.2.4.1. Change from Baseline in Frequency and Severity of Abdominal Pain and Abdominal Discomfort

The weekly abdominal pain and the weekly abdominal discomfort rate for each subject will be computed, as described in [Section 3.3.7](#), for each week of the 4-week treatment period and for the two weeks of the follow-up period. A summary, by treatment group, of the mean weekly abdominal pain and abdominal discomfort rate and change from baseline in mean weekly abdominal pain and abdominal discomfort rates, for each of the 6 study weeks will be presented. The change from baseline in mean weekly abdominal pain and abdominal discomfort rates will be analyzed using a linear mixed-effects ANCOVA model with fixed effects for gender (stratification variable), treatment, week, the interaction of treatment and week, and the corresponding baseline value; a random intercept for subject will also be specified. The least squares (LS) mean change from baseline will be presented, by treatment groups, and the difference in LS means for each treatment group versus placebo and combined active doses within each age group versus placebo in a separate model for each age group, and overall active doses versus placebo in a separate model with 95% confidence intervals and corresponding statistical p-values.

The weekly average abdominal pain and abdominal discomfort scores will be determined using the approach defined in [Section 3.3.7](#) with missing scores excluded as described in [Section 3.3.4](#) and presented for each week in the 4-week treatment period. The change from baseline in the weekly averaged abdominal pain and abdominal discomfort scores will be analyzed in the FAS Population using a linear mixed-effects ANCOVA model with fixed effects for gender (stratification variable), treatment, week, the interaction of treatment and week, and the corresponding baseline value; a random intercept for subject will also be specified. The least squares (LS) means, with 95% confidence intervals and the corresponding statistical p-value, will be presented for each week, and across all 4 weeks, of the 4-week treatment period for the difference between the difference in LS means for each of treatment group versus placebo, combined active doses within each age group versus placebo, and overall active doses versus placebo. The analysis of interest for this secondary endpoint is the difference in LS means between each plecanatide group (each dose within each age group, combined active dose within each age group, and overall active dose) versus placebo for the estimated overall average change from baseline in abdominal pain and abdominal discomfort scores across the 4-week treatment period.

Baseline abdominal pain and abdominal discomfort will be calculated as the equally weighted average of the average abdominal pain (or abdominal discomfort) for each of the two weeks prior to initiation of study drug.

The above analysis will be repeated for the PP Population.

5.2.4.2. Change from Baseline in Frequency of BMs and CSBMs, by Study Week

The weekly BM (and CSBM) rate for each subject will be computed, as described in [Section 3.3.7](#), for each week of the 4-week treatment period and for the two weeks of the follow-up period. A summary, by treatment group, of the mean weekly BM (and CSBM) rate and change from baseline in mean weekly BM (and CSBM) rate, for each of the 6 study weeks will be presented. The change from baseline in mean weekly BM (and CSBM) rate will be analyzed using a linear mixed-effects ANCOVA model with fixed effects for gender (stratification variable), treatment, week, the interaction of treatment and week, and the corresponding baseline value; a random intercept for subject will also be specified. The least squares (LS) mean change from baseline will be presented, by treatment groups, and the difference in LS means for each treatment group versus placebo and combined active doses within each age group versus placebo in a separate model for each age group, and overall active doses versus placebo in a separate model with 95% confidence intervals and corresponding statistical p-values.

The baseline BM (and CSBM) rate will be calculated as the average BM (and CSBM) rate for each of the two weeks preceding initiation of study drug.

The above analysis will be repeated for the PP Population.

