6.4.1 Packaging

Each investigational drug kit will be supplied in blister packaging. At the randomization visit (Day 1), eligible patients enrolled in treatment group A (6 to 11 years old) will receive one drug kit for the entire 4 weeks of dosing (Weeks 1, 2, 3, and 4) 28 days plus 4 additional tablets to allow for a +3-day window. Patients in treatment group B (12 to < 18 years old) will receive two drug kits and will be instructed to take one tablet from each drug kit (2 tablets daily) for the entire 4 weeks of dosing (56 tablets) plus 8 additional tablets to allow for a +3-day window. Patients will be instructed to bring their kits to the EOT or EW study visit for determination of compliance and reconciliation of supplies.

Each investigational study drug kit will contain 32 tablets. Individually blister-packaged tablets will be provided in four connected strips (of 8 tablets) as a 4-panel key-pack that folds into a carton. The two bottom panels fold up into the two top panels, nesting blister cavities. Instructions for releasing a tablet from the blister dome are printed on the outside of the carton.

Clinical sites will save all empty packaging or packaging containing unused tablets for final disposition instructions from the sponsor.

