3.3.6. Presentations by Study Visit

The daily electronic diary entries reported during the Treatment Period will be classified into 4 weeks – Week 1 (Day 1-7); Week 2 (Day 8-14); Week 3 (Day 15-21); Week 4 (Day 22-28); Week 5 (Day 29-35); Week 6 (Day 36-49).

Non-diary data, such as vital signs and clinical laboratory assessments, will be displayed and analyzed according to the nominal visit date on the eCRF unless the visit is an unscheduled visit. Unscheduled visit values will be used if the unscheduled visit falls in a visit window and the scheduled visit from the same visit window has a missing value. Visit windows will be calculated as follows for vital signs, urine pregnancy test, and physical examination:

Nominal Visit	Minimum Study Day	Maximum Study Day
Screening Week -4	-28	-1
Week 1	1	14
Week 4	15	35
Post-Treatment Week 6	36	49

Visit windows for serum chemistry, hematology, and urinalysis will be calculated as follows:

Nominal Visit	Minimum Study Day	Maximum Study Day
Screening Week -4	-28	-1
Week 1	1	14
Week 4	15	45

If assessments are collected multiple times within a given Study Visit window, the result closest to the scheduled visit date will be used for summary presentations. If two measurements have the same distance to the expected date, the latest result will be used. If a subject has multiple non-missing scheduled values on the same date, the latest result in terms of time will be used. All assessments will be presented in the listings.

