5.2.2. Primary Efficacy Analysis

The weekly SBM rate for each subject will be computed for each week of the 4-week treatment period. The change from baseline in mean weekly SBM rate will be analyzed using a linear mixed-effects model with fixed effects for gender (stratification variable), treatment, week, the interaction of treatment and week, and the corresponding baseline value; a random intercept for subject will also be specified. The least squares (LS) mean change from baseline will be presented, by treatment groups, and the difference in LS means for each treatment group versus placebo and combined active doses within each age group versus placebo in a separate model for each age group, and overall active doses versus placebo in a separate model with 95% confidence intervals and corresponding statistical p-values.

The baseline SBM weekly rate will be the weekly average number of SBMs recorded during each of the 2 weeks preceding initiation of study drug.

The above analysis will be repeated for the PP Population.

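### For the secondary frequency endpoints the treatment contrast is not limited to Weeks 1-4, and the SAP's Week 6 spans 14 days although the weekly rate is a sum over days

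*Combined protocol and SAP*

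**What the plan says.** SAP 5.2.4.2 derives BM and CSBM rates "for each week of the 4-week treatment period and for the two weeks of the follow-up period". It plans a descriptive summary by treatment group that "for each of the 6 study weeks will be presented". The mixed model that follows has fixed effects for gender, "treatment, week, the interaction of treatment and week, and the corresponding baseline value", with a random intercept, and no weeks are named. The reporting sentence, "The least squares (LS) mean change from baseline will be presented, by treatment groups", gives no averaging window either. The same pattern appears in SAP 5.2.4.1 (pain and discomfort rates), 5.2.4.6 (fecal incontinence), 5.2.4.7 (defecation-pain rate) and 5.2.4.8 (large-diameter stools). Protocol 8.8.2 is equally open for these endpoints.

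Other analyses do state a window:
- Primary endpoint (SAP 5.2.2): "The weekly SBM rate for each subject will be computed for each week of the 4-week treatment period".
- Pain and discomfort scores (second part of SAP 5.2.4.1): LS means "will be presented for each week, and across all 4 weeks, of the 4-week treatment period". Stool consistency (5.2.4.4) and the defecation-pain score (second part of 5.2.4.7) are worded the same way.
- Rescue medication (SAP 5.2.4.5): treatment period only.

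The diary windows are in SAP 3.3.6. Its sentence announces four treatment-period weeks, lists them, and continues with "Week 5 (Day 29-35); Week 6 (Day 36-49". Protocol 8.4.2 stops at Day 28. SAP 3.3.7 defines the weekly BM rate as a sum over the recorded days of the week and applies that method to the other frequency measures. Visit 4 is scheduled at Day 42 with a window of +3 days.

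**The concern.** Weeks 5 and 6 follow the last dose. If they enter the model and the treatment LS mean averages over all modelled weeks, each of the seven measures is reported as a mixture of on-drug and off-drug results. It would then not be comparable with the primary endpoint, or with the severity score for the same symptom. In 5.2.4.1 and 5.2.4.7 the rate and the score sit side by side, and only the score has a stated window.

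Even if nobody intends a six-week average, the estimand is open: two competent programmers could follow the text and produce different estimates and p-values.

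The Week 6 window is a separate fault. A sum over more than seven days is compared with a baseline on a seven-day scale, so the Week 6 change from baseline is too high in every arm, and so is the Week 6 line of the six-week summary.

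**Working it through.** The plan states no figure on this point, so there is none to reproduce.

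**Step 1. Which weeks does the text supply?**

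| Analysis | Weeks in derivation | Weeks in model sentence | Window of LS mean |
|---|---|---|---|
| Primary SBM (5.2.2) | 1-4 | none named | none named |
| Severity and consistency scores (5.2.4.1, 5.2.4.4, 5.2.4.7) | 1-4 | none named | each week and across Weeks 1-4 |
| Secondary frequencies (5.2.4.1, 5.2.4.2, 5.2.4.6-5.2.4.8) | 1-6 | none named | none named |

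In the primary analysis only the derivation sentence fixes the weeks. The same convention applied to the frequency endpoints gives six. This is an inference from the drafting, not a statement in the plan.

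**Step 2. What would a six-week LS mean estimate?** With treatment-by-week in the model, the default treatment LS mean weights the modelled weeks equally. SAP 3.3.4 fills missing frequency values with zero, so each subject has a value in every week. Let D be the on-drug difference in each of Weeks 1-4 and rD the difference in each of Weeks 5-6:

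six-week contrast / on-drug contrast = (4D + 2rD) / 6D = (4 + 2r)/6

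| Assumed r | Ratio | Loss |
|---|---|---|
| 1 (effect fully persists) | 6/6 = 1.00 | 0% |
| 0.5 | 5/6 = 0.83 | 17% |
| 0 (effect vanishes) | 4/6 = 0.67 | 33% |
| -0.5 (effect reverses) | 3/6 = 0.50 | 50% |

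The formula takes every week to be on a seven-day scale, which Step 4 shows is not guaranteed for Week 6.

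**Step 3. Check by simulation.** Sixty simulated trials (90 active, 30 placebo) had a true difference of 1.5 in Weeks 1-4 and 0 in Weeks 5-6. Mean estimated differences were:
- six-week average: 1.11
- Week 1-4 contrast from the six-week model: 1.60
- model fitted to Weeks 1-4 only: 1.60

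The ratio is 1.11/1.60 = 0.69 against an expected 0.667; the gap is simulation noise. Either route to a Week 1-4 contrast gives the same answer.

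**Step 4. Length of Week 6.**
- Window as written: 49 - 36 + 1 = 14 days.
- Diary days available if Visit 4 falls on Day 45 (42 + 3): 45 - 36 + 1 = 10 days.
- Inflation of a summed rate: 10/7 = 1.43.
- Illustration with an assumed true rate of 4 per week: 4 x 10/7 = 5.7. A subject with no change from a baseline of 4 would show a change of +1.7.

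With the last diary day at Day 42, Week 6 holds seven days and there is no error. The error therefore varies between subjects with the date of the last visit.

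**The case against.** The strongest defence is that the plan never says six weeks enter the model. The six weeks are attached to deriving the rate and to the descriptive summary. Section 5.2.4.2 is headed by study week, the model has a treatment-by-week term, and the tables planned in SAP 9.1 for these endpoints are by study week. Week-specific LS means would fit that text and would not be diluted. These are also unadjusted secondary endpoints in a trial that SAP 3.3.3 calls exploratory, and the six weekly summaries will show on-drug and off-drug results separately.

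Much of this stands: dilution needs two unstated choices, six weeks in the model and a default average over all of them. The omission remains, because the severity text asks for weekly and four-week LS means and the frequency text asks for neither.

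Four stronger readings are tempting but not supported:
- *All frequency endpoints are affected.* SBM frequency as the primary endpoint, and rescue use, are limited to the four treatment weeks.
- *A third of the effect is lost, or at most a third.* That is the case r = 0. The loss is smaller if the effect persists and larger if it reverses, and the documents give no off-treatment effect.
- *A definite loss of power follows.* The planning difference and SDs in SAP 3.1 are adult-based values for SBM frequency, the unaffected endpoint. The seven measures have no planned effect, SD or power, so no power figure can be attached.
- *Week 5 contains scheduled dosing.* Protocol 6.4.1 supplies "28 days plus 4 additional tablets to allow for a +3-day window", but Protocol 6.2 specifies four consecutive weeks of administration. Spare tablets do not establish dosing on Days 29-31, and any such dosing would reduce the dilution.

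**Conclusion.** The point holds in two parts of different strength.

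The Week 6 window is wrong as written. A 14-day window combined with a rate defined as a sum lets about 10 days count as one week when Visit 4 uses its full +3 days, a factor of up to 1.43. This assumes that the diary runs to the final visit and that the visit is held within its window.

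The missing Week 1-4 limit is an unspecified estimand for seven secondary frequency measures. Specifying it is an improvement at no cost. If the six-week default were used, the contrast would be (4 + 2r)/6 of the on-treatment effect: 67%, 83% or 100% at r = 0, 0.5 or 1. That rests on equal week weights, seven-day weeks and an assumed r. The primary result is not affected.

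**What to change.** In SAP 5.2.4.1 (rates), 5.2.4.2, 5.2.4.6, 5.2.4.7 (rate) and 5.2.4.8, state that the treatment contrast is the LS-mean difference averaged over Weeks 1-4. Obtain it either by fitting Weeks 1-4 only or by a Week 1-4 contrast in a six-week model, and say which. Report Weeks 5 and 6 separately as post-treatment results.

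In SAP 3.3.6, limit Week 6 to Days 36-42, or scale it to a seven-day rate. The first is simpler: because missing days count as zero, a scaled rate would need its own definition of the number of days to divide by. Also correct the lead-in that announces four weeks and lists six.

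The cost is SAP wording and programming, with no new data. Protocol section 8 lets the SAP supersede it on analyses other than the primary, so these secondary endpoints need only a SAP revision. It should be made before unblinding.

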5.2.4.3. Time to First BM

For the time to first BM endpoint, the distribution for each treatment group within each age group, combined active doses within age group, and overall active doses will be estimated by the Kaplan-Meier method and will be compared by the Log-rank test. The median and quartile time along with the 95% confidence limits for the median will be presented for each treatment group.

Kaplan-Meier curves with 95% confidence limits will also be presented graphically by treatment group (Age group A and B with Placebo on one page, and Combined age group with Placebo on a second page).

The above analysis will be repeated for the PP Population.

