Spontaneous bowel movement (SBM)	A bowel movement that occurs in the absence of laxative use within the preceding 24 hours
Complete spontaneous bowel movement (CSBM)	A spontaneous bowel movement with the sense of complete evacuation

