3.3.1 Permitted Concomitant Medications

Rescue Medication (RM) – Dulcolax®

Dulcolax® 5 mg tablets will be dispensed to patients at Visit 1 and resupplied as needed. From Visit 1 and for the duration of the trial, only protocol supplied Dulcolax® is to be used as the “rescue medication” (laxative) - no other laxatives are allowed. The study level allowable dosage for children age 6 to 12 years is one tablet (5 mg daily) and for children 12 years and older the dosage is 1 to 2 tablets daily (5 to 10 mg). Dulcolax® tablets must be swallowed whole.

Patients are instructed to take rescue medication only if it has been at least 72 hours since their last bowel movement. A patient is therefore expected to have no more than two days of RM use in any given week.

Each rescue medication usage will be recorded daily via the electronic diary. Clinical site personnel will review rescue medication use with patients/caregivers during their telephone contact visits and have the option to discontinue participation of patients who do not adhere to rescue medication guidelines.

Patients are advised NOT to take rescue medication for the period from 24 hours before to 72 hours after Day 1 of dosing. This avoids confounding the data collected in the first week of study drug administration and allows for accurate determination of the time to first BM. Dulcolax®. An initial supply of Rescue Medication will be provided to each site from [REDACTED]. For additional bulk supplies of rescue medication, the site will make a request through IWRS. Supplies of Dulcolax® will not be reconciled at the completion of the study. Sites must track inventory of rescue medication supplies as this will not be managed through IWRS.

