Change from baseline for a given endpoint is defined as the Study Visit value minus the Baseline Value.

Last Dose of Plecanatide

Last Dose of Plecanatide is defined as the last date that the subject received Plecanatide as determined by last date of dosing as recorded on the Study Drug Administration CRF.

Duration of Plecanatide

Duration of Plecanatide is defined as the number of days from Day 1 to the date of Last Dose of Plecanatide.

Duration on Study

Duration on study is defined as the number of days from the date of screening to the date of last follow-up visit.

Dosing Compliance

Dosing compliance will be defined by the dosing compliance ratio: the number of doses actually taken by the subject divided by the number of doses that were expected to be taken during the same period multiplied by 100.

Treatment Compliance

Treatment compliance is defined as taking equal to or greater than 80% of the drug dosage prescribed. Otherwise, the subject will be considered noncompliant with study treatment.

Rescue Medication

Dulcolax® will be provided as a rescue laxative that can be used if a subject has not had a bowel movement for at least 72 hours. Subjects will be advised that it is preferred that they do NOT take rescue medication for the period from 24 hours before to 72 hours after Day 1 of dosing.

Adverse Event

An adverse event (AE) is any untoward medical occurrence associated with the use of a drug in humans, whether or not considered to be drug related. An AE can therefore be any unfavorable and unintended sign (including abnormal laboratory finding), symptom, or disease temporally associated with the use of an investigational product or study procedure whether or not considered related to the product or procedure.

Specific gastrointestinal symptoms related to IBS-C recorded daily in the electronic Diary will be summarized separately and generally not also recorded as Adverse events.

Treatment-emergent Adverse Event

A treatment emergent adverse event (TEAE) is defined as an AE that begins or worsens in frequency and/or severity after at least one dose of study drug has been administered. Additionally, it is assumed that an Adverse Event which was reported to have started on Day 1 without an associated onset time occurred after the initiation of study drug is treatment-emergent.

Treatment-emergent Laboratory Toxicities

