5.2.3. Secondary Efficacy Endpoints

- Change from baseline in frequency and severity of abdominal pain and abdominal discomfort
- Change from baseline in frequency of BMs, SBMs, and CSBMs
- Time to First BM
- Change from baseline in stool consistency (BSFS or mBSFS-C)
- Use of Rescue Medication
- Change from baseline in frequency of fecal incontinence
- Change from baseline in frequency and severity of defecation pain
- Change from baseline in frequency of large diameter stools

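### As worded, time to first BM counts movements that follow rescue laxative and has no censoring rule, so a real drug effect would be understated in the tail of the curves and the log-rank test

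*Combined protocol and SAP*

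**What the plan says.** SAP 5.2.3 lists the secondary endpoint as "Time to First BM". SAP 5.2.4.3 begins "For the time to first BM endpoint, the distribution for each treatment group within each age group", adds the combined doses within each age group and all doses overall, and says that these "will be estimated by the Kaplan-Meier method and will be compared by the Log-rank test". Protocol 8.8.2.3 uses the same methods by treatment arm. Neither section gives an event definition, a time origin, a censoring rule or a rule for rescue.

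Both documents define an SBM as "A bowel movement that occurs in the absence of laxative use within the preceding 24 hours" (protocol Definition of Terms; SAP 3.3.7), and both name BMs, SBMs and CSBMs as distinct measures.

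Protocol 3.3.1 sets the rescue conditions: "Patients are instructed to take rescue medication only if it has been at least 72 hours since their last bowel movement". It adds: "Patients are advised NOT to take rescue medication for the period from 24 hours before to 72 hours after Day 1 of dosing", partly because this "allows for accurate determination of the time to first BM". SAP 3.3.7 words the advice as a preference, as does the protocol synopsis: "Subjects will be advised that it is preferred that they do NOT take rescue medication". Protocol 4.2.1 has the diary record when rescue was taken and how much.

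**The concern.** Rescue is meant for patients who have gone 72 hours without a BM. After dosing, those are the patients who make up the tail of the time-to-first-BM curve. When such a patient takes bisacodyl, the next BM may be the laxative's doing, yet as the endpoint is worded it is credited to the randomised arm.

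If the drug shortens the time to a spontaneous BM, more placebo than active patients reach 72 hours without one. Rescue then turns more placebo patients into events soon after that point. The log-rank test compares drug plus some rescue with placebo plus more rescue, and the difference shrinks. The protocol shows awareness of the problem in 3.3.1, and the primary endpoint avoids it by counting SBMs, but this analysis does not carry that through.

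**Working it through.** The plan states no event count, hazard ratio or power for this endpoint, so there is no figure to reproduce. What follows is an illustration.

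**Inputs from the documents.** Rescue is allowed after 72 hours without a BM (protocol 3.3.1). Group B has 90 active and 30 placebo patients (SAP 3.2, three active arms of 30 and one placebo arm of 30). Treatment lasts 28 days. The difference of 1.5 per week is borrowed from the primary-endpoint planning assumption (SAP 3.1). The 5% two-sided level is stated for the primary endpoint (SAP 5).

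**Assumptions not in the documents.** Times to first spontaneous BM are exponential with weekly rate r; the rates are 3 v 4.5 or 2 v 3.5 (placebo v active); the rescue BM comes 6 to 12 hours after the tablet; uptake among eligible patients varies. The documents give no expected rescue use and no BM rates for these patients.

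**Step 1: no BM by 72 hours.** The probability is exp(−3r/7).

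**Step 2: first BM actually produced by rescue, full uptake at 72 hours.** The rescue BM falls on average 9 hours (0.375 day) later, so the share is about exp(−3.375r/7).

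| Rate per week | No BM by 72 h | Rescue-induced first BM |
|---|---|---|
| 3 (placebo) | exp(−1.286) = 0.276 | exp(−1.446) = 0.235 |
| 4.5 (active) | exp(−1.929) = 0.145 | exp(−2.170) = 0.114 |
| 2 (placebo) | exp(−0.857) = 0.424 | exp(−0.964) = 0.381 |
| 3.5 (active) | exp(−1.5) = 0.223 | exp(−1.688) = 0.185 |

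So the rescue-induced shares are about 24% v 11% at 3 v 4.5 per week, and about 38% v 19% at 2 v 3.5.

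**Step 3: effect on the comparison.** Trials of 90 v 30 were simulated at full uptake, with any BM as the event and then with first SBM censored at rescue.

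- At 3 v 4.5 (true ratio 4.5/3 = 1.50), the hazard ratio for any BM is about 1.40. Log-rank power is about 34%, against 38% for first SBM.
- At 2 v 3.5 (true ratio 3.5/2 = 1.75), the hazard ratio for any BM is about 1.5. Power is about 46%, against 55%.
- Repeat runs put the loss at about 2 to 9 points over these two settings.
- At 30% uptake the hazard ratios are 1.45 against 1.48, and 1.66 against 1.73.

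**Step 4: medians.** The exponential median is 7·ln 2/r days. It falls before 72 hours when r > 7 × 0.693/3 = 1.62 per week. If nobody takes rescue before 72 hours, the curves are untouched up to that point, and a median below it barely changes.

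**Step 5: no drug effect.** With 3 v 3 per week the hazard ratio is about 1.0 and the rejection rate about 5% under either event definition.

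**Step 6: rescue before 72 hours after dosing.** The 72-hour rule runs from the last BM, which may precede Day 1, so some patients could qualify earlier and only the advice holds them back. If the advice is ignored (assuming a pre-dose rate of 2 per week), then at 2 v 3.5 with 70% uptake the placebo median is 1.30 days instead of 2.49 and the hazard ratio is 1.41 against 1.76. Across the settings run, which also included 1.5 v 3 per week, the power loss is about 2 to 18 points.

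**The case against.** The documents never say that a rescue-induced BM counts; the event is simply undefined. That is true. The reading rests on the endpoint's name, the separate SBM term and the absence of any exclusion, so the firm defect is the missing definition.

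The rescue advice was written with this endpoint in mind. If followed, it leaves the curves intact to 72 hours and the medians nearly so. This stands, and it rules out the broader inference that the whole curve is distorted. It does not help patients with no BM by 72 hours, and it is not binding.

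Time to any BM, with rescue as part of care, is a legitimate quantity. It is, but protocol 3.3.1 treats rescue here as confounding, so it is not evidently the quantity the sponsor wanted.

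Two stronger readings are tempting. One is that the analysis could produce a false positive; with no drug effect there is no differential shortening and the test holds its level. The other is that the effect shrinks to about 1.3. Dividing mean times at full uptake does give 1.784/1.378 = 1.30 at 3 v 4.5 and 2.166/1.630 = 1.33 at 2 v 3.5, but those are person-time rate ratios. The SAP uses the log-rank test, and the hazard ratios that match it are less attenuated.

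Finally, this is one secondary endpoint in a trial the SAP calls exploratory. The primary endpoint already uses SBMs, and rescue use is compared by arm (SAP 5.2.4.5). That limits the consequence.

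**Conclusion.** The point stands, at moderate weight. The event and censoring for time to first BM are undefined, and the plain wording includes BMs after rescue. If the drug works and rescue is used, the tail of the curves and the log-rank test are pulled toward no difference.

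At full uptake from 72 hours, the hazard ratio falls from 1.50 to about 1.40, or from 1.75 to about 1.5, with about 2 to 9 points of power lost. The effect is smaller at lower uptake and larger if rescue is taken before 72 hours. These sizes rest on assumed exponential times, BM rates and uptake; the documents supply none of them. The direction needs only a working drug and rescue use under the 72-hour rule. The documents do not support a claim of type I error inflation, or of shifted medians where the advice is followed and the placebo rate is above about 1.6 SBMs per week.

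**What to change.** Amend SAP 5.2.4.3 before unblinding, since a definition chosen afterwards would be open to the charge of being data-driven:

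- Main analysis: time from first dose to first SBM, using the SAP's existing definition, censored at first rescue use after dosing. Patients with neither are censored at their last diary day in the 28-day treatment period.
- Supportive analysis: time to first BM of any kind, as now named.
- Log-rank test stratified by gender within each age group, and by gender and age group in the overall comparison, to match the randomisation.

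The cost is SAP wording and some programming. Rescue times are already in the diary, and no visit, procedure or rescue instruction changes. The downside is that censoring at rescue may be somewhat informative if the decision to take it depends on symptoms and not only on elapsed time. That is the reason for keeping the any-BM analysis alongside.
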